8.2 Recording / Reporting requirements

8.2.1 Eliciting adverse event information:

Participants will be routinely observed and questioned about adverse events during their visits.

8.2.2 Recording requirements:

All observed or volunteered adverse events (serious or non-serious) and abnormal test findings, regardless of study group or suspected causal relationship to the study drug(s) will be recorded in the subjects’ case histories. For all adverse events, sufficient information will be pursued and/or obtained so as to permit 1) an adequate determination of the outcome of the event (i.e., whether the event should be classified as a *serious adverse event*) and; 2) an assessment of the casual relationship between the adverse event and the study drug(s).

Adverse events or abnormal test findings felt to be associated with the study drug(s) will be followed until the event (or its sequelae) or the abnormal test finding resolves or stabilizes at a level acceptable to the Sponsor-Investigator.

8.2.2.1 Abnormal test findings:

An abnormal test finding will be classified as an *adverse event* if one or more of the following criteria are met:

The test finding is accompanied by clinical symptoms

The test finding necessitates additional diagnostic evaluation(s) or medical/surgical intervention; including significant additional concomitant drug treatment or other therapy

Note: simply repeating a test finding, in the absence of any of the other listed criteria, does not constitute an adverse event.

The test finding leads to a change in study drug dosing or discontinuation of subject participation in the clinical research study

The test finding is considered an adverse event by the Sponsor-Investigator of the IND application

8.2.2.2 Causality and severity assessment:

The Sponsor-Investigator of the IND application will promptly review documented adverse events and abnormal test findings to determine 1) if the abnormal test finding should be classified as an adverse event; 2) if there is a reasonable possibility that the adverse event was caused by the study drug(s); and 3) if the adverse event meets the criteria for a *serious adverse event*.

If the Sponsor-Investigator's final determination of causality is "unknown and of questionable relationship to the study drug(s)", the adverse event will be classified as *associated with the use of the study drug(s)* for reporting purposes. If the Sponsor-Investigator's final determination of causality is "unknown but not related to the study drug(s)", this determination and the rationale for the determination will be documented in the respective subject's case history.

9. Statistical methods/Data Analysis:

Clinical symptoms and Laboratory parameters will be analyzed using appropriate statistical method.

9.1 Study endpoints:

9.1.1 Primary endpoints:

- a) Measuring International Prostate Symptom Score
- b) Prostate Specific Antigen test

SYMPTOM SCORE - IPSS SCORE *

INTERNATIONAL PROSTATE SYMPTOM SCORE SHEET								
[name]:		Address:						
Patient Name:		Address:						
Date:						
Age Group:		40-49 	50-59 					
		60-69 	70+ 					
		Not at all	Less than 1 time in 5	Less than half the time	About half the time	More than half the time	Almost always	Your score
1. INCOMPLETE EMPTYING	Over the past month, how often have you had a sensation of not emptying your bladder completely after you finished urinating?	0	1	2	3	4	5	
2. FREQUENCY	Over the past month, how often have you had to urinate again less than two hours after you finished urinating?	0	1	2	3	4	5	
3. INTERMITTENCY	Over the past month, how often have you found you stopped and started several times when you urinated?	0	1	2	3	4	5	
4. URGENCY	Over the past month, how often have you found it difficult to postpone urination?	0	1	2	3	4	5	
5. WEAK STREAM	Over the past month, how often have you had a weak urinary stream?	0	1	2	3	4	5	
6. STRAINING	Over the past month, how often have you had to push or strain to begin urination?	0	1	2	3	4	5	
7. NOCTURIA	Over the past month, how many times did you most typically get up to urinate from the time you went to bed at night until the time you got up in the morning?	None 0	1 time 1	2 times 2	3 times 3	4 times 4	5 or more times 5	
Which of the above do you regard as most troublesome [1-7] _____								
TOTAL PROSTATE SYMPTOM SCORE _____								
		Delighted	Pleased	Mostly satisfied	Mixed - satisfied and dissatisfied	Mostly dissatisfied	Unhappy	Terrible
QUALITY OF LIFE DUE TO URINARY SYMPTOMS	If you were to spend the rest of your life with your urinary condition just the way it is now, how would you feel about that? (tick one).	0	1	2	3	4	5	6

*International Prostate Symptom Score

IPSSymptom Score= sum of questions A1 to A7

- ◆ Mild Score : 0-7
- ◆ Moderate Score: 8-19
- ◆ Severe Score: 20-35

The Assessment will be made before and after treatment by calculating the International Prostate Symptom Score. Based on this the clinical condition may be divided into mild, moderate and severe. The response will be categorized as mentioned above.

9.1.2 Secondary endpoints:

Measuring Siddha clinical parameters like Envagai thervu, Neerkkuri and Neikkuri

11. Data Handling and Record-Keeping:

11.1 Data recording / Case Report Forms:

A Case Report Form (CRF, see Appendix 1) will be completed for each subject enrolled in the clinical study. The Sponsor-Investigator will review, approve and sign/date each completed CRF; the Sponsor-Investigator's signature serving as attestation of the Sponsor-Investigator's responsibility for ensuring that all clinical and laboratory data entered on the CRF are complete, accurate and authentic.

Source Data are the clinical findings and observations, laboratory and test data, and other information contained in *Source Documents*. *Source Documents* are the original records (and certified copies of original records); including, but not limited to, hospital medical records, physician or office charts, physician or nursing notes, subject diaries or evaluation checklists, pharmacy dispensing records, recorded data from automated instruments, x-rays, etc. When applicable, information recorded on the CRF shall match the *Source Data* recorded on the *Source Documents*.

12. Ethics:

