The current medical practice produces serious side effects such as Impotence, decreased libido, decreased quantity of semen at ejaculation, gynecomastia, asthenia, hypotension, dizziness, somnolence, fatigue, dyspnea and upper respiratory tract infection. When medication fails surgical intervention is needed but this is costly in practice. Moreover, at present herbal remedies like Saw Palmetto (*Serenoa repens*) produces good results in reducing the complaints of the BPH patients. Literary evidences reveal Siddha formulations are being practiced since ages. In exploring the efficacy of Siddha medication for this particular condition evaluation of a new investigational drug is indispensable.

1.2 Rationale:

The investigational new drug (IND) though a classical preparation, is going to be tested for new indication. So it falls under new chemical entity (NCE). Hence, as per AYUSH guidelines safety study is intended. The approval will be sought from the Institutional Animal Ethical Committee and the Safety studies will be done at Department of Pharmacology, SCRI, Chennai.

Another drug XXX is taken up for another one arm and its efficacy is compared with that of XXX. XXX is a well known Siddha drug and it is in practice since time immemorial. Its indication suits the clinical condition Neer kattu (Retention of urine). Since it is a classical drug which is going to be put into trial, preclinical study is not mandatory. [Ref: ICMR Guidelines& WHO Guidelines]

A sample size of twenty patients from OPD of CCRS Institutes will be randomized and put in two arms as open labeled study. The suitable participants as per inclusion criteria will be enrolled and the trial drugs will be administered orally as mentioned in the classical reference. The duration of the trial period will be three months.

BPH is a common condition that affects aged men. The prevalence of BPH is about 50% of men between 50 to 60 years and more than 90% of men who are older than 80 years old. However, only 25% of men above 50 and 50% of men above 75 are symptomatic.²

Benign prostatic hyperplasia (BPH) is a histological diagnosis that refers to the proliferation of smooth muscle and epithelial cells within the prostatic transition zone. It is the most common benign tumor in men and is not a precancerous condition.

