The eligible participants will be enrolled according to the inclusion criteria. The full details of the history and physical examination of the patient will be recorded as per the Proforma (Form 1 & 2) Clinical Assessment will be done on 0, 15, 30,45,60,75 and 90th days (Form 3). Laboratory investigations will be recorded as per the proforma (Form 4) before treatment (0 day), after treatment (at the end of 3rd 6th and 9th month).

6.2 Study drug procedures:

The study arm 1 will receive 100mg of drug with milk q.s after food at morning and night.

The study arm 2 will receive 60 ml of decoction before food at morning and night.

6.3 Follow-up procedures:

Follow ups in both arms will be carried out after 45th and 90th day after completion of 3 months treatment period.

6.4. Schedule of activities (Study table):

Type of study	Randomized, comparative, open labeled clinical study									
Phase	2									
Sample size	20 [without including drop outs, lama]									
Randomization	By appropriate method									
Study arms	Arm 1 => 10 subjects					Arm 2 => 10 subjects				
Intervention	xxx – 100 mg bid with milk after food					xxx- 60 ml bid before food				
Study period	6 months [3 months drug therapy + 3 months follow up]									
Visits		At initial visit (0)	I visit (15 th day)	II visit (30 th day)	III visit (45 th day)	IV visit (60 th day)	V visit (75 th day)	VI visit (90 th day)	Follow up 6 th month	Follow up 9 th month
Arm 1	10 subjects	Screening	Measuring IPSS and other Clinical data	Reporting ADR if any	Reporting ADR if any					
Laboratory investigations		USG,PSA test and other investigations						USG,PSA test and other investigations		
Arm2	10 subjects	Screening	Measuring IPSS and other Clinical data	Reporting ADR if any	Reporting ADR if any					
Data compilation	Data compiled for preparing monograph. Research article will be communicated after compiling the data.									

Safety and Effectiveness Assessments:

7.1 Safety assessment:

Blood and Urine examination will be done to evaluate the safety of the study drug. Laboratory investigations will be recorded as per the proforma (Form 4) before treatment (0 day), after treatment (at the end of 3rd 6th and 9th month).

7.2 Effectiveness assessment:

The IPSS, ultra sonogram study and test for PSA range will be done according to the proforma.

8. Adverse Event Reporting:

8.1 Adverse event definitions:

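### Follow-up to resolution is promised only for adverse events that an unblinded investigator judges drug-related, so recovery and duration of the other events are not guaranteed and may be unevenly complete between arms

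*Protocol*

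**What the plan says.** Protocol Section 8.2.2 (Recording requirements) makes three statements that need to be read together.

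- **Recording.** All adverse events and abnormal findings, "regardless of study group or suspected causal relationship to the study drug(s) will be recorded in the" case histories.
- **Information on every event.** This applies to each event without exception: "sufficient information will be pursued and/or obtained so as to permit 1) an adequate determination of the outcome of the event". A causality assessment must be possible as well. A bracket explains outcome as "whether the event should be classified as a" serious adverse event.
- **Follow-up.** The commitment is worded: "Adverse events or abnormal test findings felt to be associated with the study drug(s) will be followed until the event". It ends once the event, including any after-effects, or the finding has cleared or has settled at a point that satisfies the Sponsor-Investigator.

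The surrounding text matters too. Section 3.3 declines blinding. Section 8.2.2.2 gives the causality decision to the Sponsor-Investigator and names no blinded or independent assessor. Section 6 describes the trial as a comparison of both safety and efficacy between the two drugs, and safety of the investigational drug is a secondary objective.

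**The concern.** Recording does not depend on the causality opinion, but the promise of follow-up does. The person who forms that opinion knows which drug the man received. Two men with the same symptom could therefore have different follow-up guarantees: one followed until the symptom has gone or settled, the other with an entry showing that it occurred, how serious it was and what was thought to have caused it, but not necessarily whether or when he recovered.

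What is at stake is the resolution status and duration of events judged unrelated. If the causality opinion is applied differently in the two arms, these data will be more complete in one arm than in the other, and a comparison of how events ended would partly reflect the opinion. An event that looks unrelated when it stands alone, but would look different once similar cases appear, is among those without the guarantee.

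**Working it through.** The protocol gives no figure on this point, so there is nothing to recompute. The check sets out what Section 8.2.2 and its neighbours guarantee for an event, according to the causality opinion.

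| Item | Judged drug-associated | Judged unrelated | Where stated |
|---|---|---|---|
| Occurrence recorded | Yes | Yes | 8.2.2 |
| Seriousness determined | Yes | Yes | 8.2.2, 8.2.2.2 |
| Causality assessed | Yes | Yes | 8.2.2, 8.2.2.2 |
| Followed until resolved or stable | Yes | No commitment | 8.2.2 |
| Resolution status required | Implied by the follow-up rule | Not stated | 8.2.2 |

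**Step 1: does the all-events sentence close the gap?** It would if outcome meant recovery. The bracket ties it to the seriousness classification instead. An event can be classed correctly as serious or non-serious without anyone recording whether it resolved.

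**Step 2: does the default for doubtful cases close it?** Section 8.2.2.2 treats a doubtful relationship as associated, which narrows the excluded group. The text limits this to reporting and does not extend it to follow-up. An event of unknown cause judged not related needs only a documented rationale.

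**Step 3: do the scheduled visits close it?** During treatment, largely. Section 8.2.1 has all men questioned about adverse events at their visits, which Section 6.1 places every 15 days to day 90. After treatment the cover is weaker:

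- As extracted, the Section 6.4 table gives only adverse drug reactions as the reporting task at the follow-up visits. Section 8.1 defines an adverse reaction as an event caused by a drug, so the causality condition returns.
- Form III stops at day 90 and has no adverse-event or resolution column.
- Sections 6.1 and 7.1 repeat laboratory tests at months 3, 6 and 9 irrespective of causality, but the table shows them only at entry and day 90. The table was read by a program and may be broken. Laboratory tests would in any case not show the course of symptoms.

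**Step 4: is the final visit fixed?** Section 6.3 says: "Follow ups in both arms will be carried out after 45th and 90th day after completion of 3 months treatment period". Taking the end of treatment as day 90, that is 90 + 45 = day 135 and 90 + 90 = day 180, which agrees with the six-month participation stated in the study design section and in the table's own study-period row. The same table also heads its follow-up columns the 6th and 9th months, about 6 × 30 = day 180 and 9 × 30 = day 270. The two final dates differ by 270 − 180 = 90 days. A follow-up rule that ends at the final visit needs this settled.

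**The case against.** The strongest reply is that Section 8.2.2 excludes nothing. It is silent on follow-up of unrelated events, and much of their course will be seen anyway through visits, questioning and repeat laboratory tests. Seriousness is itself defined in Section 8.1 partly by outcomes such as death and persistent incapacity, and information on these must be sought for every event. What lacks a guarantee is therefore mainly the resolution and duration of non-serious events judged unrelated. No endpoint listed in Section 9.1 uses either. The case report form (Appendix 1) and Form 4 are not in the supplied text, so a resolution field may already exist. All of this stands, and it limits the point to guarantee and completeness.

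Three stronger readings are tempting, but the documents do not support them.

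- *That outcomes of unrelated events are lost.* The text makes no commitment for them; it does not say that they go unfollowed.
- *That Arm 1 events are more likely to be followed.* Section 1.2 does say of the comparator that "XXX is a well known Siddha drug and it is in practice since time immemorial", and plans a safety study for the investigational drug. But that study is preclinical, is prompted by the new indication and expresses no suspicion of harm. Section 1.1 describes the investigational preparation as widely used, and Section 3.3 calls both drugs classical. A team hopeful about its investigational drug could equally judge its events unrelated. Attribution could differ in either direction.
- *That the arms are under different rules, or that incidence is distorted.* One rule covers both arms; only its application could differ. Every event is recorded, so counts do not depend on this sentence.

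**Conclusion.** The point holds in a limited form. Follow-up to resolution or stabilisation is guaranteed only for events and findings that an unblinded Sponsor-Investigator attributes to a study drug, and nothing else in the protocol clearly guarantees it for the rest. Resolution and duration of events judged unrelated may be incomplete, and the degree of incompleteness could differ between arms. Counts, seriousness and causality assessments are captured for every event and are not affected.

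No numerical size can be given. The protocol states neither expected event numbers nor attribution rates by arm, so any percentage would be invented. The conclusion rests on reading the bracket after outcome as it is written, and on no unseen form already requiring resolution status for every event. It is a modest weakness in secondary safety data, worth correcting because the correction is cheap and removes an opinion-dependent condition from a safety comparison that Section 6 says the trial will make.

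**What to change.** Replace the follow-up sentence in Section 8.2.2 with wording to this effect:

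*Every adverse event in either arm, whatever its suspected cause, is followed until it resolves or stabilises or until the final study follow-up visit, whichever comes first. Adverse events and abnormal test findings judged associated with a study drug, including findings not classed as adverse events, are followed until resolved or stable, beyond that visit if necessary.*

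The second sentence keeps the protection that the current text gives to drug-associated abnormal findings. After the final visit a causality condition remains, but by then every event has a status recorded on the same terms in both arms.

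Three consequential changes are needed:

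- Replace the bracket after outcome with a resolution status for each event (resolved, resolved with sequelae, ongoing, fatal), and record seriousness as a separate item.
- Reconcile the date of the final follow-up visit between Section 6.3, the six-month study period and the 9th-month column of the Section 6.4 table.
- Have the follow-up visits in that table report all adverse events, not only adverse drug reactions.

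The cost is one reworded passage, one status field and a few more follow-up entries among 20 men. The post-treatment visits are already planned for both arms, so none is added.

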- c) To assess the effect in the level of PSA, if any.
- d) Exploring Siddha clinical parameters of the clinical condition *Purasthakola perukkam* [BPH].

2. Study Design:

[figure not shown]
Open clinical study

[Randomized, comparative open labeled clinical study]

Since the trial is in two arms, to avoid the bias in the study participants, randomization is opted. The efficacy will be compared with the known Siddha drug XXX. The indication tried with that of XXX is a novel idea, Henceforth the baseline study will be of open labeled.

The expected total duration of subject participation will be six months. Data summarization, Statistical analyzing and monograph preparation will need additional three months. The drug therapy will be of 12 weeks. The follow up will be done without drug on 45th day and 90th day.

3.1 Study design schematic:

3.2 Allocation to treatment:

This clinical study involves two arms. The sample size of subjects is 20. 10 subject each in a single arm. They will be randomized by appropriate method.

3.3 Breaking the blind:

Blinding is not opted as both the trial drugs are classical preparations. The making of placebo is little bit difficult. The study comes under Phase II category. There is lack in published data. Hence an open clinical study is designed.

4. Subject selection:

The proposed clinical evaluation of the investigational new drugs will be done in the OPD's of peripheral Institutes of CCRS. The estimated total number of individuals to be enrolled in this clinical study will be twenty. The subjects to be enrolled will be provided with patient information sheet and informed consent form.

4.1 Subject inclusion criteria:

- Male patients between 40 and 75 years of age.
- Patient diagnosed with BPH and with clinical signs and symptoms of BPH for 3 months.
- Confirmed diagnosis: a) Ultra sonogram study
b) Prostatic Specific Antigen Score 4 ng to 8 ng /mL
[Normal range-PSA Score 0.8 to 4 ng /mL]
- Patient having a post-void residual urine volume of 350 cc.
- Participants who adhere to protocol requirements with written informed consent.

4.2 Subject exclusion criteria:

- PSA score beyond acceptable range and patients with a history of prostate cancer or a serum PSA >8 ng/mL [will be excluded by reviewing the past medical history and the current medication]
- History of urinary urethral obstruction due to stricture, valves, sclerosis or tumor at initiation
- Clinical evidence of prostate cancer at initiation

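### The rule that turns an abnormal test into an adverse event (8.2.2.1) has no new-or-worse-than-day-0 condition, so the raised PSA required for entry can be counted as an adverse event in any man who stays above 4 ng/mL and symptomatic

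*Protocol*

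**What the plan says.** **The rule.** Protocol 8.2.2.1: "An abnormal test finding will be classified as an *adverse event* if one or more of the following criteria are met". The first criterion is "The test finding is accompanied by clinical symptoms". The others concern further diagnostic work-up or intervention, a change in dosing or discontinuation, and the Sponsor-Investigator's own opinion. One note narrows the rule: "simply repeating a test finding, in the absence of any of the other listed criteria, does not constitute an adverse event".

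**Who enters.** Section 4.1 requires "Patient diagnosed with BPH and with clinical signs and symptoms of BPH for 3 months", ultrasound confirmation and "Prostatic Specific Antigen Score 4 ng to 8 ng /mL". Beside the PSA criterion it gives the reference range: "Normal range-PSA Score 0.8 to 4 ng /mL".

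**What is repeated.** Section 7.2: "The IPSS, ultra sonogram study and test for PSA range will be done according to the proforma". The study table in 6.4 lists ultrasound and PSA at the initial visit and once after baseline. Sections 6.1 and 7.1 schedule laboratory investigations "before treatment (0 day), after treatment (at the end of 3rd 6th and 9th month").

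**Use of the events.** Safety of the investigational drug is secondary objective (a) and a secondary outcome in Section 6. PSA is a primary endpoint in 9.1.1.

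**The concern.** An adverse-event count should reflect what happens to a man after he starts the drug. This rule instead asks whether a test is abnormal and symptoms are present. In this population that describes the qualifying disease. A man whose PSA and symptoms stand still, or improve without normalising, meets it.

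Three things follow. Baseline disease can enter the safety count. An efficacy measure can drive that count, because an arm in which PSA falls below 4 ng/mL more often would show fewer adverse events for that reason alone. And if staff drop such findings by unwritten judgement, they do so knowing the arm, since the trial is open label. Section 8.2.2.2 adds to this: an event whose cause is unknown and questionable is reported as associated with the study drug.

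**Working it through.** The protocol states no expected adverse-event rate, PSA change or symptom change, so there is no figure to reproduce. The check has two parts.

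**1. The wording, applied to illustrative records**

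| Day 0 | After treatment | Change | First criterion, read literally |
|---|---|---|---|
| PSA 6.0, IPSS 18 | PSA 6.0, IPSS 17 | essentially none | met: adverse event |
| PSA 7.0, IPSS 20 | PSA 5.0, IPSS 10 | both improved | met: adverse event |
| PSA 4.5, IPSS 12 | PSA 3.8, IPSS 9 | both improved | not met on PSA |

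The follow-up IPSS values of 17 and 10 fall in the moderate band (8 to 19) of 9.1.1, so these men remain symptomatic. At entry itself, every man with PSA above 4 already satisfies the criterion; a PSA of exactly 4 is on the boundary. The note about repeated tests does not help, because it applies only when no other criterion is met, and here one is.

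**2. How many men it could reach**

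From the protocol: 20 men, entry PSA 4 to 8, upper normal limit 4. Assumed: entry PSA either uniform on 4 to 8 or triangular with its peak at 4; a common PSA change of 0, -10, -25 or -50%; within-man coefficient of variation (CV) 0, 15 or 30%; 100, 80 or 50% still symptomatic; one post-baseline test.

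Share meeting the rule = P(PSA > 4) × P(symptomatic), taken as independent.

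Without noise there is a closed form. For a proportional change c, P(PSA > 4) = (8 - 4/(1 + c))/4 for the uniform case, and the square of that for the triangular case. At c = -0.25, 4/0.75 = 5.33, giving (8 - 5.33)/4 = 0.67 and 0.67² = 0.44. Simulation adds the noise. Ranges over both shapes and all CVs, with men of 20 in brackets:

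| PSA change | 100% symptomatic | 80% symptomatic | 50% symptomatic |
|---|---|---|---|
| none | 75–100% (15–20) | 60–80% (12–16) | 37–50% (7–10) |
| -10% | 64–89% (13–18) | 51–71% (10–14) | 32–44% (6–9) |
| -25% | 43–67% (9–13) | 34–53% (7–11) | 21–33% (4–7) |
| -50% | 0–16% (0–3) | 0–13% (0–3) | 0–8% (0–2) |

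A second version for no change and all men symptomatic puts noise in both measurements (twice the variance), CV 10 to 30%, and entry PSA uniform or 4 plus an exponential of mean 1.5 cut off at 8. It gives 71 to 94%, or 20 × 0.71 = 14 to 20 × 0.94 = 19 men. The two versions together give about 14 to 20 of 20 when little changes.

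**Efficacy leaking into safety.** With uniform entry PSA, no noise and 80% symptomatic, an arm with no PSA change has 0.80 × 1.00 = 80% flagged, and an arm with a 25% fall has 0.80 × 0.67 = 53%. The 27-point gap would look like a safety difference with no harm in either arm.

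**With a baseline condition.** Unchanged PSA with unchanged symptoms contributes 0 of 20.

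**The case against.** The strongest reply is that 8.2.2.1 should not be read alone.

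- **Section 8.1** defines an adverse event as something untoward and associated with use of the drug. A PSA that qualified a man before dosing fits poorly, and a falling PSA is hardly untoward. This makes the literal outcome less certain. But the same sentence applies whether or not the event is thought drug related, so it is not a causality filter, and it does not mention baseline.
- **Section 8.2.2.2** has the Sponsor-Investigator determine whether an abnormal finding should be classified as an adverse event. That suggests discretion. Yet 8.2.2.1 supplies the criteria for that decision in mandatory terms, and its last criterion only lets the Sponsor-Investigator add events. At best the sections conflict.
- **Sections 7.1 and 7.2** place PSA and ultrasound under effectiveness. True, but 8.2.2.1 covers any abnormal test finding and exempts neither.
- **The first criterion** could mean symptoms arising with the abnormal result. The text does not say so.
- **The statistical analysis plan**, not shown, may define how events are tabulated. It would not change a classification rule that the protocol applies at the site.

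A reader might infer that most participants will become adverse events, that incidence will approach 100% in both arms, or that a real difference between the drugs will be hidden. The documents do not support these as facts. The first two need PSA and symptoms to change little. The third also needs event rates, and a single any-event comparison, that the protocol does not state; events are assessed individually for cause and seriousness, so a listed PSA result need not mask a different kind of event. Nor can a persisting ultrasound finding be counted with confidence, because no threshold for an abnormal ultrasound is given.

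**Conclusion.** The concern holds in conditional form. Section 8.2.2.1 lacks a baseline condition, and the entry criteria guarantee that nearly every man starts with an abnormal PSA and symptoms. Any man who remains above 4 ng/mL and symptomatic can therefore be counted as an adverse event although unchanged or improved.

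The size is not fixed by the documents. It is about 14 to 20 of 20 if PSA is unchanged and all men stay symptomatic; at most about 10 if only half stay symptomatic; and 0 to 3 after a 50% fall in PSA. The PSA changes, CVs, entry distributions and symptom shares are all assumptions. The defect in the wording, and its conflict with 8.2.2.2, do not depend on them.

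**What to change.** - In the lead-in of 8.2.2.1, limit the rule to abnormal findings that are new or have worsened from day 0.
- Reword the first criterion to: *accompanied by new or worsened clinical symptoms*.
- State that PSA, ultrasound and urinary findings present at entry as part of the qualifying BPH count as adverse events only if they worsen from day 0.
- Reconcile 8.2.2.1 with 8.2.2.2: say whether the criteria bind the Sponsor-Investigator's determination or only guide it.

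All abnormal findings continue to be recorded under 8.2.2.

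**Cost.** A few sentences and no new data, since day 0 values are already collected. Staff must compare each abnormal result with day 0. Random variation will put some unchanged men above their day 0 value, so the text should also say what counts as worsening. Persistent abnormalities that have not worsened leave the adverse-event count but stay in the case history. Because the lead-in governs every criterion, the sponsor should confirm that this is also intended for an unchanged finding that prompts intervention or discontinuation.
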